8.4 Safety and Tolerability Assessments

All patients who receive study treatment will be evaluated for safety. Safety assessments will include incidence of AEs, suicidality assessment by the C-SSRS, mania assessment by the YMRS, movement disorder assessment by the AIMS, BARS and SAS, clinical laboratory evaluations, ECG evaluations, vital sign measurements, and physical examination and neurological findings according to Appendix A (Schedule of Events).

8.5 Laboratory Procedures/Evaluations

8.5.1 Clinical Laboratory Evaluations

Blood and urine samples collected from patients will be forwarded to a central laboratory for analysis. Further details regarding sample collections, processing and specific testing can be found in the study reference manual.

All samples for clinical laboratory analysis will be collected after an overnight fast (≥10 hours), after any scheduled ECG or vital signs have been recorded, and prior to dosing with study treatment. Samples for clinical laboratory analysis will be used only for the evaluation of safety and tolerability.

Any abnormal laboratory test results (hematology, clinical chemistry, or urinalysis) or other safety assessments (e.g., ECGs, vital sign measurements), including those that worsen from baseline, felt to be clinically significant, in the medical and scientific judgment of the investigator, are to be recorded as AEs or SAEs.

However, any clinically significant safety assessments that are associated with the underlying disease, unless judged by the investigator to be more severe than expected for the patient's condition, are not to be reported as AEs or SAEs.

The following clinical analytes will be determined:

Hematology: hematocrit; hemoglobin; HbA_{1c} (only at screening V1 and end of study treatment V8); red blood cell count with indices (mean corpuscular volume, mean corpuscular hemoglobin, and mean corpuscular hemoglobin concentration); reticulocytes; white blood cell count and differential (neutrophils, lymphocytes, monocytes, eosinophils, and basophils) reported as percent (%) and absolute values; and platelets (platelet count, prothrombin time and partial thromboplastin time).

Clinical chemistry: albumin; alkaline phosphatase; blood urea nitrogen; gammaglutamyl transferase; calcium; creatinine; glucose; insulin; cholesterol (high-density lipoprotein and low-density lipoprotein [LDL] [calculated] and homogenous LDL will be reported, and homogenous LDL will be reflexed if a patient's triglycerides are >400); triglycerides; phosphate; potassium; prolactin; ALT; AST; lactate dehydrogenase; sodium; chloride; bilirubin (total, direct); total protein; uric acid; creatine phosphokinase; and thyroid panel (at screening only, thyroid-stimulating hormone will be assayed and if the result is abnormal, the free thyroxine and free triiodothyronine will be assayed).

Urinalysis: macroscopic (pH, specific gravity, glucose, protein, ketones, nitrates, blood) and microscopic – report only if present (red blood cells/high-power field, white blood cells/high-power field, casts, epithelial cells, crystals, granulation).

Serology: anti-HIV antibodies, hepatitis B surface antigen, and hepatitis C antibody (only during screening).

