9.1.10 Adverse Events

The investigator is responsible for reporting all AEs that are observed or reported during the study, regardless of their relationship to study treatment or their clinical significance.

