9.1.10.1 Definition of Adverse Event

An AE is any untoward medical occurrence in a study patient administered a study treatment, whether or not considered drug related. This can be any unfavorable and unintended sign (such as an abnormal laboratory finding), symptom, or disease temporally associated with the use of a study treatment, without any judgment of causality.

The AE may be:

- A new illness;
- A worsening sign or symptom of the condition under treatment, or of a concomitant illness;
- An effect of the study medication, including comparator; or
- A combination of 2 or more of these factors.

No causal relationship with the study medication or with the clinical study itself is implied by the use of the term AE.

Surgical procedures themselves are not AEs; they are therapeutic measures for conditions that require surgery. The condition for which the surgery is required may be an AE. Planned surgical measures, if permitted by the clinical study protocol and the conditions leading to those measures are not AEs.

All AEs fall into the categories of "nonserious" or "serious" (Section 9.1.4).

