9.1.11 Serious Adverse Events

9.1.11.1 Definition of Serious Adverse Event

An SAE is defined as any untoward medical occurrence that at any dose:

- Results in death;
- Is life threatening;
- Requires hospitalization or prolongation in existing hospitalization;
- Results in persistent or significant disability or incapacity; or
- Is a congenital anomaly or birth defect.

The term "life threatening" refers to an event in which the patient is at risk of death at the time of the event; it does not refer to an event, which hypothetically might have caused death if it were more severe.

Medical and scientific judgment should be exercised in deciding whether an AE is serious. Some important medical events that may not result in death, be life threatening, or require hospitalization may be considered SAEs when they may jeopardize the patient such that medical or surgical intervention is needed to prevent 1 of the outcomes previously listed. Examples of such medical events include intensive emergency treatment for an allergic reaction, blood dyscrasias or convulsions that do not result in inpatient hospitalization, and the development of drug dependency or drug abuse.

Visits to urgent care or emergency room facilities may not warrant reporting as SAEs unless the patient is admitted to the hospital or the event meets other "serious" criteria. Events that are not clearly meeting "serious" criteria can be discussed on a case by case basis with the Medical Monitor to help the investigator determine whether the event meets "serious" criteria.

If either the sponsor or principal investigator believes that any event is serious, the event must be considered and evaluated by the sponsor for possible expedited reporting.

Clarification of the difference between "serious" and "severe":

The term "severe" is often used to describe the intensity (severity) of a specific event (as in mild, moderate, or severe myocardial infarction); the event itself, however, may be of relatively minor medical significance (such as a severe headache). This is not the same as "serious," which is based on patient/event outcome or action criteria usually

associated with events that pose a threat to a patient's life or functioning. Seriousness (not severity) serves as a guide for defining regulatory reporting obligations.

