9. DISPOSITION AND WITHDRAWALS

Subject disposition and withdrawals will be presented by treatment group, when applicable, and overall for the ENR Set.

The number and percentage of subjects who were screened, screen failed, randomized, completed or discontinued the 6-week On-Treatment Period and completed or discontinued the study, and reasons for treatment discontinuation and study discontinuation will be presented. The reasons for study withdrawal and treatment discontinuation are listed in Table B:.

The reasons for treatment discontinuation will also be presented by treatment group and by time to treatment discontinuation, categorized based on the planned visits (≤ Day 8, > Day 8 -

Document: ...\ITI\ITI-007\MYA11638\Biostatistics\Documentation\SAP\ITI-007-404 SAP Final V1.0 12JUN2019.docx Author: Version Number:1.0

Page 18 of 53

 \leq Day 15, > Day 15 - \leq Day 22, > Day 22 - \leq Day 29, > Day 29 - \leq Day 36, > Day 36 - \leq Day 43) for all subjects in the SAF Set. The reasons for study discontinuation and treatment discontinuation are listed in Table B.

A subject is defined to have completed treatment if the subject completed the 6-week On-Treatment period as recorded on the End of Treatment CRF page.

A subject is defined to have completed the study if the subject has completed the 6-week On-Treatment Period and the end of study follow-up assessments as recorded on the End of Study CRF page.

Reasons for Study Withdrawal and Study Medication Discontinuation Table B: **Terminology**

| Case Report Form Terminology | Study | Study Medication |
|---|-------|---------------------|
| Screen failure | Х | |
| Adverse event | X | Х |
| Adverse event associated with worsening of bipolar depression* | X | X |
| Adverse event not associated with worsening of bipolar depression* | X | X |
| Death | Х | Х |
| Lack of efficacy | Х | X |
| Lost to Follow-up | Х | |
| Protocol violation | Х | X |
| Physician decision | Х | X |
| Study terminated by sponsor | Х | X |
| Subject withdrew consent: | Х | X |
| Personal or family reasons; | X | X |
| Refused to provide a reason or refused all end-of-study procedures; | X | X |
| Self-reported adverse event; | X | X |
| Self-reported lack of efficacy | X | X |
| Other | Х | Х |

^{*} Adverse event associated with worsening of bipolar depression will be identified by a Medical Monitor review prior to database lock.

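### Protocol 8.5.1 bars sites from reporting disease-associated safety findings as AEs or SAEs unless the investigator thinks them worse than expected, and Section 9 contains no such exemption

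*Protocol*

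**What the plan says.** Protocol 8.5.1 (Clinical Laboratory Evaluations) first sends abnormal results to AE or SAE recording. It covers laboratory tests "or other safety assessments (e.g., ECGs, vital sign measurements), including those that worsen from baseline, felt to be clinically significant" by the investigator. The next paragraph makes an exception: "However, any clinically significant safety assessments that are associated with the underlying disease, unless judged by the investigator to be more severe than expected" for that patient's condition, "are not to be reported as AEs or SAEs".

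Protocol 8.4, a little earlier, describes what the safety assessments include. Besides AE incidence, laboratory tests, ECGs and vital signs, it names "suicidality assessment by the C-SSRS, mania assessment by the YMRS".

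Section 9 sets the reporting duty in different terms:

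- 9.1.10: the investigator reports all AEs, "regardless of their relationship to study treatment or their clinical significance".
- 9.1.10.1: an abnormal laboratory finding is given as an example of a sign that can be an AE, and the list of what an AE may be includes "A worsening sign or symptom of the condition under treatment, or of a concomitant illness".
- 9.1.11.1: an event is serious if it meets any listed criterion, one of which is "Requires hospitalization or prolongation in existing hospitalization". There is no exemption for the disease under study.
- 9.1.9, 9.4 and 9.4.2: all SAEs are recorded from consent to follow-up, all AEs go on the eCRF, and SAEs reach the sponsor within 24 hours.

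**The concern.** The two parts of the protocol give sites opposite instructions for the same finding. Section 8.5.1 adds two filters that Section 9 lacks: whether the finding is linked to the underlying disease, and whether it is worse than the investigator expected. Neither filter is defined there, and about 70 sites would each apply them by judgment.

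This matters in a bipolar depression trial because the scales that 8.4 calls safety assessments measure mania and suicidality, and both are naturally described as associated with bipolar disorder. A site following 8.5.1 to the letter could leave such a finding off the AE page when it regards the finding as expected. AE and SAE counts could then differ by site for reasons unrelated to treatment, and a finding that met a seriousness criterion could miss the 24-hour route to the sponsor.

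**Working it through.** No figure in the documents bears on this point, so there is nothing to calculate. The check is whether one finding can satisfy both sets of rules.

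| Question | Protocol 8.5.1 | Protocol Section 9 |
|---|---|---|
| Does a link to the underlying disease remove the duty to report? | Yes, unless worse than expected | No (9.1.10, 9.1.10.1) |
| Is there an expectedness threshold for reporting? | Yes, set by the investigator | No (9.1.10, 9.1.11.1) |
| Does meeting a seriousness criterion override the exemption? | No; the bar names SAEs | No exemption exists to override (9.1.11.1) |

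Four cases show where the conflict falls.

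1. **A clinically significant YMRS or C-SSRS finding, disease-related and judged expected.** Under 9.1.10.1 a worsening of the treated condition can be an AE, and 9.1.10 then requires it to be reported. Under 8.5.1, read with the list in 8.4, it is not to be reported. Both rules cannot be followed.
2. **A laboratory, ECG or vital-sign finding, disease-related, judged expected and meeting a seriousness criterion.** Under 9.1.11.1 it is an SAE and 9.4.2 starts the 24-hour clock. Under 8.5.1 it is not to be reported as an SAE. The conflict remains even when the exemption is read as narrowly as its examples allow.
3. **A finding judged worse than expected.** Section 8.5.1 keeps it reportable, so there is no conflict.
4. **Worsening depression on the MADRS.** Section 8.2.1 treats the MADRS as an efficacy assessment, and 8.4 does not list it. Section 8.5.1 does not directly reach it.

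The worse-than-expected exception does not resolve case 2. Section 9.1.11.1 itself explains that seriousness concerns outcome and severity concerns intensity, so an event can be serious without being more intense than anticipated. Section 9.3.2 does use an expectedness test, but there the sponsor or its designee classifies SAEs against the Investigator's Brochure. In 8.5.1 the test is the investigator's, is made against the patient's condition, and decides whether anything is reported at all.

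The last step is what would still be seen if a finding were withheld. SAP 16.6.1 summarizes observed YMRS scores and changes by treatment and visit. SAP 16.6.5 tabulates C-SSRS ideation and behavior, including emergence and, for ideation, worsening, without relying on AE coding. These data stay visible. The AE or SAE record, its place in the TEAE and SAE tables, and the 24-hour report would be missing.

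**The case against.** The best defense is about scope. The paragraph sits in the laboratory section and qualifies a sentence whose only named examples are ECGs and vital signs. The C-SSRS and YMRS are specified elsewhere (8.1.7, 8.1.8, 9.1.1, 9.1.2). A hospitalization or a manic episode is a medical occurrence, not an assessment, and a site dealing with one would probably turn to Section 9, where the duty is stated repeatedly. This makes the narrow reading reasonable and limits the likely practical effect. It does not make that reading the only one, because the wording covers any safety assessment and 8.4 says what those include. It also leaves case 2 unresolved.

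The second defense is the exception. Entry requires a YMRS total of 12 or less (inclusion 3e) and excludes C-SSRS ideation items 4 or 5 and a MADRS item 10 score of 4 or more (exclusion 2). In patients selected this way, a manic switch or new ideation at level 4 or 5 would often count as worse than expected and so stay reportable under 8.5.1 itself. That stands. A reader might infer a flat ban on reporting mania and suicidality, and the documents do not support that. The gap is limited to findings judged expected.

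A reader might also infer that 8.5.1 suppresses reports of worsening depression. Case 4 shows that it does not do so directly. Protocol 12.4.1 and SAP Section 9 plan to count discontinuations due to such events, and a note to SAP Table B says: "Adverse event associated with worsening of bipolar depression will be identified by a Medical Monitor review prior to database lock". That plan presupposes that sites record them as AEs.

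Nor can it be said that withheld findings would escape the blinded safety review. Protocol 10.1 has that review look at outlier safety parameters and other relevant parameters as well as AEs.

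**Conclusion.** The contradiction is real and needs correcting. For a clinically significant finding that is disease-associated and judged expected, 8.5.1 forbids a report that Section 9 requires. The literal wording can reach YMRS and C-SSRS findings of that kind. On the narrow reading, the bar on SAE reporting still has no exception for findings that meet a seriousness criterion.

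The possible loss is confined to AE and SAE counts and 24-hour SAE reporting. The YMRS and C-SSRS data are not lost. The documents give no event rate, no indication of how sites would apply the paragraph and no basis for a difference between arms, so any count of unreported events would be invention. The conclusion rests on the text alone. It assumes only that some sites would follow 8.5.1 as written.

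**What to change.** The sponsor should reconcile 8.5.1 with Section 9 in one of two ways:

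- delete the paragraph that begins with the exemption; or
- limit it to non-serious laboratory, ECG or vital-sign findings that are part of an AE already reported.

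With either option, 8.5.1 should state that 9.1.10.1 and 9.1.11.1 govern all AE and SAE reporting, including findings from the YMRS and C-SSRS.

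The cost is a short protocol amendment, a memo to sites and slightly more AE records. No new assessments or analyses are needed.

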8.5.2 Hepatitis Screening

Blood samples will be collected at screening from all patients in order to perform hepatitis B surface antigen and hepatitis C antibody (immunoglobulin G) testing. Test results will be sent to the screening site and must be reviewed before the Day 1 visit. Any patient who tests positive for hepatitis B or C will be excluded from participating in the study. Details regarding sample collection, processing, and shipping can be found in the study reference manual.

8.5.3 HIV Screening

Patients are required to provide blood samples for HIV virus types 1 and 2 testing. Test results will be sent to the screening site and must be reviewed before the Day 1 visit. Any patient who tests positive for HIV will be excluded from participating in the study. Patients will be informed of positive HIV results and referred for follow-up testing and counseling, and health authorities will be notified of positive HIV results consistent with federal, state, and local laws. Details regarding sample collection, processing, and shipping can be found in the study reference manual.

8.5.4 Urine Drug and Alcohol Screening

Qualitative urine drug (amphetamines, barbiturates, benzodiazepines, cannabinoids [THC], cocaine metabolites, methadone, opiates, phencyclidine, propoxyphene) and alcohol tests will be performed. Any patient who tests positive for drugs of abuse or alcohol test at the screening visit, or presents evidence of either withdrawal from or acute intoxication with cocaine, opiates, amphetamines (including methamphetamine), alcohol, barbiturates, or hallucinogens or similar compounds will be excluded. The urine drug screen may be repeated once based on investigator judgment and reviewed for medical appropriateness by the Medical Monitor as part of the screening adjudication process.

Note: Previous occasional use of alcohol or cannabis (but not synthetic marijuana/K2/Spice) or prescribed psychotropic (e.g., benzodiazepine, opiate) is allowed as long as the level of use does not meet DSM-5 criteria for any moderate or severe substance use disorder within the 12 months prior to screening and the use of alcohol or cannabis is not considered to be the precipitating factor of the current depressive episode, in the opinion of the investigator and any prescribed psychotropic is accompanied by evidence of prescription; patients are required to abstain from alcohol and drug use during the study.

Further information regarding sample collection, processing, and shipping can be found in the study reference manual.

		5		
		23		
0				
0				
			24	
				24
-				
		a		
20 D.S.	_			
		8173	8121	141Z)
2			14105	1000
	3 — 1	and a		
		and a		
		14 N		
2.0 °		2		
×				
5				

9 ASSESSMENT OF SAFETY

9.1 Specification of Safety Parameters

9.1.1 C-SSRS

The C-SSRS will be completed at screening, baseline, and at every subsequent scheduled clinic visit according to Appendix A (Schedule of Events). Details of the C-SSRS are presented in Section 8.1.7.

9.1.2 YMRS

The YMRS will be completed at screening, baseline, and at every subsequent scheduled clinic visit according to Appendix A (Schedule of Events). Details of the YMRS are presented in Section 8.1.8.

9.1.3 Abnormal Involuntary Movement Scale

The AIMS (Guy 1976) measures facial and oral movements, extremity movements, and trunk movements. Seven items are rated on a scale from none (0) to severe (4). A score of "mild" (2) in 2 or more categories or a score of "moderate" or "severe" in any 1 category results in a positive AIMS score (i.e., the scores are not averaged). Additionally, overall severity is scored on the basis of severity of abnormal movements and incapacitation due to abnormal movements. The patient's awareness of and distress caused by the abnormal movements are also noted. The AIMS is to be completed at baseline and periodically throughout the study according to Appendix A (Schedule of Events).

9.1.4 Barnes Akathisia Rating Scale

The BARS is a rating scale for drug-induced akathisia developed by Barnes (1989). It includes the rating of observable restless movements, the subjective awareness of restlessness, and the distress associated with the akathisia. There is also a global rating for severity. The scale is completed by the investigator or an expert site-based rater after a standard examination. Objective akathisia, subjective awareness and subjective distress are rated on a 4-point scale from 0 to 3, yielding a total score from 0 to 9. The Global Clinical Assessment of Akathisia is rated separately, on a 5-point scale from 0 to 4. The BARS is to be completed at baseline and periodically throughout the study according to Appendix A (Schedule of Events).

9.1.5 Simpson-Angus Scale

The SAS is a measure of extrapyramidal side effects (Simpson and Angus 1970). Ten items including rating gait, arm dropping, shoulder shaking, elbow rigidity, wrist rigidity, leg pendulousness, head rotation, glabella tap, tremor, and salivation are rated on a scale from 0 (normal) to 4 (extreme in severity). The SAS should be conducted by the

investigator or an expert site-based rater in a room where the patient can walk a sufficient distance to allow a natural pace (e.g., 15 paces). Each side of the body should be examined. The SAS is to be completed at baseline and periodically throughout the study according to Appendix A (Schedule of Events).

9.1.6 Vital Sign Measurements

Vital signs will be measured at screening and at subsequent scheduled clinic visits according to Appendix A (Schedule of Events). Details of the vital sign measurements are presented in Section 8.1.5.

9.1.7 ECG Assessments

The ECG assessments will be performed at screening and periodically throughout the study, according to Appendix A (Schedule of Events). Details of the ECG assessments are presented in Section 8.1.4.

9.1.8 Physical and Neurological Examination

The physical and neurological examinations will be conducted at screening and periodically throughout the study, according to Appendix A (Schedule of Events). Details of the physical and neurological examinations are presented in Section 8.1.3.

9.1.9 Unanticipated Problems

The investigator will review each SAE (Section 9.1.4) and evaluate the intensity and the causal relationship of the event to study treatment. All SAEs will be recorded from signing of informed consent until follow-up.

The investigator is responsible for providing notification to the sponsor or designee of any SAE, whether deemed related to study treatment or not, that a patient experiences during their participation in study within 24 hours of becoming aware of the event.

As a minimum requirement, the initial notification should provide the following information:

- Study number
- Patient number
- Gender
- Date of birth
- Name of investigator and full study site address

- Details of SAE
- Criterion for classification as "serious"
- Study treatment code, or name if unblinded, and treatment start date and stop date, if applicable
- Date of SAE onset
- Causality assessment (if sufficient information is available to make this classification)

The sponsor will request clarification of omitted or discrepant information from the initial notification. The investigator or an authorized delegate is responsible for transmitting (via fax or email) the requested information to the sponsor within 24 hours of the sponsor's request.

Initial reports of SAEs must be followed later with detailed descriptions, including clear photocopies of other documents as necessary (e.g., hospital reports, consultant reports, autopsy reports), with the study patient's personal identifiers removed. All relevant information obtained by the investigator through review of these documents will be recorded and transmitted to the sponsor within 24 hours of receipt of the information. If a new SAE Report Form is transmitted, then the investigator must sign and date the form. The sponsor may also request additional information on the SAE, which the investigator or an authorized delegate must transmit to the sponsor within 24 hours of the request.

The SAE reporting contact information will be provided to all participating study sites by the contract research organization (CRO) before study initiation.

The Office for Human Research Protections (OHRP) considers unanticipated problems involving risks to patients or others to include, in general, any incident, experience, or outcome that meets **all** of the following criteria:

- unexpected in terms of nature, severity, or frequency given (a) the research procedures that are described in the protocol-related documents, such as the IRB/IEC-approved research protocol and informed consent document; and (b) the characteristics of the patient population being studied;
- related or possibly related to participation in the research ("possibly related" means there is a reasonable possibility that the incident, experience, or outcome may have been caused by the procedures involved in the research); and

 suggests that the research places patients or others at a greater risk of harm (including physical, psychological, economic, or social harm) than was previously known or recognized.

